5 METHODOLOGY

5.1 Overall Study Design

This is a prospective, randomized, controlled, multicenter, clinical investigation.

5.1.1 Objectives

The objective of this pivotal clinical investigation is to evaluate the safety and efficacy of a new hemostatic device (HEMOBLAST™) compared to G+T.

5.2 Primary Efficacy Endpoint

The primary efficacy endpoint of this clinical investigation is non-inferiority of HEMOBLAST™ relative to G+T for success at achieving hemostasis within 6 minutes.

5.3 Secondary Efficacy Endpoints

The secondary efficacy endpoints of this clinical investigation are:

- Superiority of HEMOBLAST™ relative to G+T in mean preparation time from the opening of package to product being ready to use;
- Non-inferiority of HEMOBLAST™ relative to G+T for success at achieving hemostasis within 3 minutes;
- Superiority of HEMOBLAST™ relative to G+T for success at achieving hemostasis within 6 minutes; and
- Superiority of HEMOBLAST™ relative to G+T for success at achieving hemostasis within 3 minutes.

5.4 Additional Exploratory Outcomes

The additional exploratory outcomes of this clinical investigation that will be described and quantified are:

- Operative time for HEMOBLAST™ subjects compared to G+T subjects;
- Duration of hospitalization for HEMOBLAST™ subjects compared to G+T subjects; and
- Number of units of blood transfused intraoperatively for HEMOBLAST™ subjects compared to G+T subjects.

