6 INVESTIGATIONAL PROCEDURES

6.1 Schedule Overview

Table 3 details the clinical investigation visits, corresponding timing, and evaluations to be performed at the visit. Table 4 lists the CRFs that need to be completed at each visit. Figure 1 represents the subjects' participation in the clinical investigation.

Table 4. Investigational Evaluation Schedule

[figure not shown]
Visit	Timing	Evaluations
Preoperative	Within 4 weeks before surgery	Informed consent, preoperative eligibility criteria confirmation, preoperative evaluations, and blood draw for antibody evaluation
Intraoperative	Day of surgery; day 0	Intraoperative inclusion criteria confirmation, efficacy assessments, and safety assessments
Postoperative	Postoperative day 1	Safety assessments
6 Week Follow-Up	6 weeks (± 2 weeks) postoperatively	Safety assessments, blood draw for antibody evaluation, and study discontinuation

Table 5. CRF Completion Schedule

CRF	Screening	Preoperative	Intraoperative	Postoperative	Follow-Up	Discontinuation
Preoperative Eligibility CRF	X					
Preoperative CRF		X				
Intraoperative CRF			X			
Concomitant Medication CRF		O	O	O	O	
Laboratory CRF		X		X		
Postoperative CRF				X		
Follow-Up CRF					X	
Discontinuation CRF						X
Adverse Event CRF			O	O	O	
Device Deficiency CRF			O			
Reoperation CRF				O	O	

X	Mandatory
O	As applicable

Figure 1. Subject Participation in the Clinical Investigation

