6.3 Preoperative Procedures and Evaluations

The following data will be collected and recorded at the preoperative visit on the Preoperative CRF:

- Demographic data;
 - Age,
 - Gender,
 - Race and ethnicity,
- Physical exam and laboratory tests;
 - Height,
 - Weight,
 - Diastolic and systolic blood pressure,
 - CBC (Laboratory CRF),
 - Coagulation status (Laboratory CRF),
 - Chemistry panel (Laboratory CRF),
 - Pregnancy test for females of child-bearing age (Laboratory CRF),
 - Blood draw for antibody testing,
- Medical history; and
 - Coagulation disorder(s),

- History of bleeding requiring hospitalization in the last five years,
- Disease process / indication for surgery,
- Concomitant illnesses,
- Surgical history related to the surgical area,
- Diabetes,
- Smoking history,
- Malignancies and prior therapies,
- Hepatic disease,
- Concomitant medications potentially impacting coagulation status (Concomitant Medication CRF).

The Laboratory CRF will be completed and applicable concomitant medications will be recorded on the Concomitant Medication CRF. A blood draw for antibody testing will be performed and handled per specified procedures agreed upon with the investigational site and core laboratory.

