6.4.1 Intraoperative Inclusion Criteria

A subject must then meet all of the following intraoperative inclusion criteria:

- Subject does not have an active or suspected infection at the surgical site;
- Subject undergoing cardiothoracic surgery with anticoagulation must have anticoagulation reversed prior to TBS identification and treatment;
- Subject in whom the Investigator is able to identify a TBS for which any applicable conventional means for hemostasis are ineffective or impractical; and
- Subject has a TBS with an SBSS score of 1, 2, or 3.

If all of these intraoperative eligibility criteria are met, then the subject is formally randomized and enrolled into the clinical investigation (unless the subject is a lead-in subject; all lead-in subjects will receive HEMOBLAST™).

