12.3.2.2 Methods of Analysis

Summaries of the number and percent of subjects with at least one SAE will be provided. Comparisons of the proportion of subjects experiencing SAEs will be made between treatment arms. Summaries of the number of percent of AEs will be provided for each treatment arm.

Differences in mean overall blood loss, mean volume of intra-operative transfusions, mean total operative time, and mean duration of hospitalization will be estimated using linear regression models with stratified adjustment for surgery type and separated by surgery type. In all cases, the robust variance estimator will be used and a 95% Wald-based interval will be computed. Comparisons of the incidence of re-operation (total and reoperation due to bleeding) and the incidence post-surgery bleeding complications will be made using a general linear model to estimate the difference in the probability of each outcome after stratified adjustment for surgery type. Comparisons of the incidence of re-operation and the incidence post-surgery bleeding complications within each surgery type will be made using a two sample binomial test of proportions.

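### The intraoperative transfusion model adjusts only for surgery type; adding the preoperative hemoglobin value, which should already be on a mandatory form, would give a small, nearly free gain in precision

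*Protocol*

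**What the plan says.** **Outcome.** Protocol 5.4 and SAP 10.8 list "Number of units of blood transfused intraoperatively for HEMOBLAST™ subjects compared to G+T subjects" among outcomes to be described and quantified, with no model. Protocol 12.1.3 and SAP 10.6.2 list the mean volume of intraoperative transfusions among the safety endpoints.

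**Model.** Protocol 12.3.2.2, repeated in SAP 10.6.2, says "mean volume of intra-operative transfusions, mean total operative time, and mean duration of hospitalization will be estimated using linear regression models with stratified adjustment". The factor adjusted for is the type of surgery, and further models are fitted within each type. It adds that "the robust variance estimator will be used and a 95% Wald-based interval will be computed". No other covariate is named.

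**Population.** These models run on the Full Analysis Population: treated randomised subjects plus all lead-in subjects (Protocol 12.3.2.1, SAP 10.6.1). Lead-in subjects number at most 50, all receive HEMOBLAST and none is randomised (Protocol 6.4.2).

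**Baseline blood count.** Protocol 6.3 puts a CBC on the preoperative list and says "The Laboratory CRF will be completed and applicable concomitant medications will be recorded on the Concomitant Medication CRF". Table 5 marks the Laboratory CRF as mandatory at that visit, and Table 4 times the visit as "Within 4 weeks before surgery". Randomisation comes later, in the operating room: once the intraoperative criteria are met, "then the subject is formally randomized and enrolled into the clinical investigation" (Protocol 6.4.1).

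**Status.** Comparisons outside the fixed sequence are exploratory (Protocol 12.2.4, SAP 10.10). Transfusion is outside it.

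**The concern.** A covariate measured before assignment cannot be affected by treatment. If it predicts the outcome, including it in a linear model narrows the interval for the treatment difference. Hemoglobin before surgery is a natural candidate for a transfusion outcome, and the eligibility criteria limit platelets and INR but not hemoglobin, so baseline anemia may vary freely. The plan collects the blood count and then leaves it out of every model and subgroup. It is not among the baseline characteristics named in Protocol 12.2.6 either, so an imbalance might not be displayed.

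At stake is the width of one safety interval, and how far that estimate carries a chance difference in baseline anemia against a control arm of 133. The lead-in subjects add a second reason: they enter the HEMOBLAST group without randomisation, so balance is not protected for them.

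**Working it through.** **The plan's own figures.** The documents give no standard deviation, effect size, power or precision for transfusion, so there is nothing to reproduce on this outcome. The stated 80.1% power concerns the primary endpoint. It reproduces as 80.0% with the Table 9 boundaries and futility obeyed, and does not bear on this point.

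**Inputs.** 267 HEMOBLAST and 133 G+T randomised (Protocol 6.4.2). With 50 lead-ins the safety comparison is at most 317 against 133, N = 450. The correlation ρ between hemoglobin and transfusion within surgery type is assumed.

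**Baseline precision, in units of the residual SD.**
- Safety population: √(1/317 + 1/133) = 0.1033; 95% half-width 1.96 × 0.1033 = 0.2025 SD.
- Randomised subjects only: √(1/267 + 1/133) = 0.1061; half-width 0.208 SD.

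**Effect of adding hemoglobin.** The surgery-type model has 4 coefficients (intercept, arm, two surgery-type terms); hemoglobin makes 5. The standard error is multiplied by √[(1 − ρ²)(N − 4)/(N − 5)]. At N = 450 the degrees-of-freedom part is √(446/445) = 1.0011.

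| Assumed ρ | √(1 − ρ²) | SE ratio | Half-width (SD) | Change in width |
|---|---|---|---|---|
| 0 | 1.0000 | 1.0011 | 0.2027 | +0.1% |
| 0.15 | 0.9887 | 0.9898 | 0.2004 | −1.0% |
| 0.20 | 0.9798 | 0.9809 | 0.1986 | −1.9% |
| 0.30 | 0.9539 | 0.9550 | 0.1934 | −4.5% |
| 0.50 | 0.8660 | 0.8670 | 0.1756 | −13.3% |

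For ρ of 0.15 and 0.30 the gain equals about 2% and 10% more subjects (1/0.9898² = 1.02; 1/0.9550² = 1.10). With the 400 randomised subjects alone the percentages are the same to one decimal.

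**Break-even.** The ratio falls below 1 once ρ² exceeds 1/(N − 4): 1/446 = 0.0022, or 1/396 = 0.0025 for randomised subjects only.

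**Check on skewed counts.** Transfusion is likely to be zero for many subjects. A simulation of zero-heavy unit counts (400 subjects, 1,500 trials per setting, 24% to 29% transfused; all settings assumed) included three settings in which hemoglobin was predictive. Partial R² was 0.021, 0.061 and 0.096, that is ρ of about 0.14, 0.25 and 0.31. The empirical SE ratios were 0.995, 0.960 and 0.964, so the SE fell by about 0.5% to 4%. This is why 0.15 to 0.3 is the working range.

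**Imbalance.** The randomised arms' difference in mean hemoglobin has SE 0.106 SD, so 0.2 SD is within 1.96 SE. It would move the transfusion contrast by ρ × 0.2: 0.03 SD at ρ = 0.15 and 0.06 SD at ρ = 0.3, against a half-width of 0.208 SD. For lead-ins, suppose their mean hemoglobin differs from that of randomised subjects by 0.5 SD (an assumption). The HEMOBLAST mean then shifts by 50/317 × 0.5 = 0.079 SD, and the contrast by 0.3 × 0.079 = 0.024 SD at ρ = 0.3.

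**The case against.** The strongest reply is that this is a preference and not a defect. The planned model is valid, is already adjusted for surgery type with a robust variance, and serves an exploratory comparison with no precision target. SAP 10.8 also permits ad hoc exploratory analyses. The validity and the exploratory status stand, and they keep the point at the level of a free improvement. The ad hoc allowance does not answer it: a covariate chosen after the data are seen carries less weight than one named in advance.

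The premise can also be challenged. Neither document names hemoglobin or says how strongly it predicts transfusion. Reading it into the CBC is reasonable, but its prognostic strength is a clinical expectation, and a value up to four weeks old may predict less well. This stands, and is why only a range is given.

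A reader might infer three stronger things. One is that the planned estimate is biased or wrong; among randomised subjects it is neither. Another is that 400 subjects could act like 533, which is 400/(1 − 0.5²); that needs a correlation of 0.5, for which the documents give no basis and which exceeds anything in the simulation. The third is that transfusion is almost the only bleeding measure not scored on the SBSS. The plan also lists overall blood loss, reoperation for bleeding, post-surgery bleeding complications and postoperative blood products.

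Finally, Protocol 5.4 speaks of units and gives no model, while 12.3.2.2 models mean volume. The documents do not say that the units outcome uses that model.

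**Conclusion.** The point holds as a minor, nearly free improvement to Protocol 12.3.2.2 and SAP 10.6.2. For an assumed within-surgery-type correlation of about 0.15 to 0.3, the interval for mean transfusion volume would be roughly 1% to 5% narrower. Larger gains need a higher correlation; with none, the SE cost is about 0.1%. Adjustment would also remove the part of any hemoglobin imbalance that a linear term captures, including imbalance brought in by lead-in subjects. It does not make those subjects equivalent to randomised ones.

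This rests on the CBC including hemoglobin, on a roughly common linear slope in both arms, and on the assumed correlation. The success criterion, the interim analysis and the fixed sequence are unaffected.

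**What to change.** In Protocol 12.3.2.2 and SAP 10.6.2:
- Add preoperative hemoglobin (last Laboratory CRF value before surgery, continuous) to the intraoperative transfusion model beside surgery type.
- Keep the robust variance and Wald interval, and show the surgery-type-only estimate next to the adjusted one.
- State how a missing value is handled, for example by substituting the surgery-type mean computed without regard to arm.
- State whether the models within each surgery type also take the covariate. With about 450/3 = 150 subjects each, its cost if uninformative is still only √(148/147) = 1.003.

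In Protocol 5.4 and SAP 10.8, reconcile number of units with mean volume and say that the same model applies.

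The cost is one regression term and a few sentences, with no new data, visit or subject. The change should be made before treatment-arm results are seen.

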5.5 Subject Selection Criteria

A maximum of 450 (400 efficacy, maximum of 50 lead-in) subjects undergoing elective open cardiothoracic, abdominal, and orthopedic lower extremity surgeries will be enrolled into the clinical investigation. Subjects will need to meet all eligibility criteria to be enrolled into the investigation, as detailed below.

5.5.1.1 *Preoperative Inclusion Criteria*

A subject must meet all of the following preoperative inclusion criteria to be enrolled into the investigation:

- Subject is undergoing an elective open cardiothoracic, abdominal, or orthopedic lower extremity surgery;
- Subject or an authorized legal representative is willing and able to give prior written informed consents for investigation participation;
- Subject undergoing cardiothoracic surgery is not allergic to protamine; and
- Subject is 21 years of age or older.

5.5.1.2 *Preoperative Exclusion Criteria*

A subject must not meet any of the following preoperative exclusion criteria to be enrolled into the investigation:

- Subject is undergoing a laparoscopic, thoracoscopic or robotic surgical procedure;
- Subject is undergoing a neurologic surgical procedure;
- Subject is undergoing a spinal surgical procedure;
- Subject is undergoing an emergency surgical procedure;
- Subject is pregnant, planning on becoming pregnant during the follow-up period, or actively breast-feeding;
- Subject has a clinically significant coagulation disorder or disease, defined as a platelet count < 100,000 per microliter or International Normalized Ratio > 1.5 within 4 weeks of surgery;
- Subject receiving intravenous heparin within 12 hours before surgery or oral Coumadin within 2 days before surgery;
- Subject receiving antiplatelet medications within 5 days prior to surgery;
- Subject undergoing abdominal or orthopedic lower extremity surgery receiving aspirin within 7 days prior to surgery;
- Subject has an active or suspected infection at the surgical site;
- Subject has had or has planned to receive any organ transplantation;
- Subject has a known sensitivity or allergy to bovine and/or porcine substance(s) or any other component(s) of the hemostatic agent;
- Subject has ASA classification of 5³;
- Subject has a life expectancy of less than 3 months;
- Subject has a known psychiatric disorder, which in the opinion of the Principal Investigator, would preclude the subject from completing this clinical study;
- Subject has a documented severe congenital or acquired immunodeficiency;
- Subject has religious or other objections to porcine, bovine, or human components;
- Subject in whom the investigational or control device will be used at the site of a valve replacement or repair;
- Subject in whom the investigational or control device will be used at the site of a synthetic graft or patch implant;

³ ASA Classification: 1 – normal health patient; 2 – patient with mild systemic disease; 3 – patient with severe systemic disease; 4 – patient with severe systemic disease that is constant threat to life; 5 – moribund patient who is not expected to survive with the operation; 6 – a declared brain-dead patient whose organs are being removed for donor purposes

- Subject is currently participating or has participated in another clinical trial within the past 30 days and is receiving/has received an investigational drug, device, or biologic agent; and
- Subject is not appropriate for inclusion in the clinical trial, per the medical opinion of the Principal Investigator.

5.5.1.3 Intraoperative Inclusion Criteria

A subject must meet all of the following intraoperative inclusion criteria to be enrolled into the investigation:

- Subject does not have an active or suspected infection at the surgical site;
- Subject undergoing cardiothoracic surgery with anticoagulation must have anticoagulation reversed prior to Target Bleeding Site (TBS) identification and treatment;
- Subject in whom the Investigator is able to identify a TBS for which any applicable conventional means for hemostasis are ineffective or impractical; and
- Subject has a TBS with an SBSS score of 1, 2, or 3.

Table 3. Enrollment Based on SBSS Score

SBSS Score	0	1	2	3	4	5
Verbal Descriptor	None	Minimal	Mild	Moderate	Severe; not immediately life-threatening	Extreme; immediately life-threatening
Visual Descriptor	Dry	Oozing	Pooling	Flowing	Streaming	Gushing
Expected Intervention(s)	None	Manual pressure, cautery, adjuvant hemostat(s)	Manual pressure, cautery, suture, adjuvant hemostat(s)	Manual pressure, cautery, suture, adjuvant hemostat(s)	Manual pressure, cautery, suture, staples, tissue repair	Manual pressure, cautery, suture, staples, tissue repair
Maximum Expected ACS-ATLS Shock Risk Class	1	1	1	2	3	4
Eligible for Enrollment	No	Yes	Yes	Yes	No	No

5.6 Point of Enrollment

All patients presenting to the Investigator for elective (non-emergent) open cardiothoracic, abdominal, or orthopedic lower extremity surgical procedures are potential study subjects and should be screened for eligibility. Subjects will need to meet all eligibility in order to be enrolled into the investigation.

A subject is enrolled when he/she meets all preoperative inclusion/exclusion criteria, signs the informed consent forms, and meets the intraoperative inclusion criteria. The point of enrollment into the clinical investigation will occur intraoperatively.

5.7 Withdrawal Criteria

Subjects may withdraw from the clinical investigation at any time without providing a reason. Subjects will not be penalized nor lose any benefits to which they are otherwise entitled if they should choose to withdraw. The Investigator may also choose to withdraw the subject if he or she feels that this is in the subject's best interest.

The possible situations for subject withdrawal will be managed as such:

- Subjects who withdraw from the study after receiving investigational device will be followed for safety through the end of the study if they agree. Efforts will be made to collect any final data and information regarding the reason for withdrawal. Data collected prior to withdrawal from the study may be used in in study analyses; or
- Subjects who withdraw from the study before receiving investigational device receive routine care. No study-specific safety or efficacy assessments will be conducted.

5.8 Subject Compliance

Every reasonable effort will be made to maintain subject compliance and participation in the clinical investigation until final follow-up is completed.

Subject loss to follow-up is not expected to impact the efficacy analysis, as the efficacy endpoints are collected intraoperatively. However, it is still important for subjects to complete the 6 ± 2 week follow-up to assess safety. The investigational site will make all reasonable efforts to contact those subjects who do not return for the 6 ± 2 week follow-up visit to collect as much follow-up information as possible to assess investigational device safety.

6 INVESTIGATIONAL PROCEDURES

6.1 Schedule Overview

Table 3 details the clinical investigation visits, corresponding timing, and evaluations to be performed at the visit. Table 4 lists the CRFs that need to be completed at each visit. Figure 1 represents the subjects' participation in the clinical investigation.

Table 4. Investigational Evaluation Schedule

[figure not shown]
Visit	Timing	Evaluations
Preoperative	Within 4 weeks before surgery	Informed consent, preoperative eligibility criteria confirmation, preoperative evaluations, and blood draw for antibody evaluation
Intraoperative	Day of surgery; day 0	Intraoperative inclusion criteria confirmation, efficacy assessments, and safety assessments
Postoperative	Postoperative day 1	Safety assessments
6 Week Follow-Up	6 weeks (± 2 weeks) postoperatively	Safety assessments, blood draw for antibody evaluation, and study discontinuation

Table 5. CRF Completion Schedule

CRF	Screening	Preoperative	Intraoperative	Postoperative	Follow-Up	Discontinuation
Preoperative Eligibility CRF	X					
Preoperative CRF		X				
Intraoperative CRF			X			
Concomitant Medication CRF		O	O	O	O	
Laboratory CRF		X		X		
Postoperative CRF				X		
Follow-Up CRF					X	
Discontinuation CRF						X
Adverse Event CRF			O	O	O	
Device Deficiency CRF			O			
Reoperation CRF				O	O	

X	Mandatory
O	As applicable

Figure 1. Subject Participation in the Clinical Investigation

6.2 Screening Evaluations

6.2.1 Informed Consent

Prior to performing any study specific procedures, a detailed explanation of the study procedures, potential discomforts, risks and benefits of participation, and alternatives will be reviewed with potential study subjects by a qualified member of the study team. The informed consent process will follow applicable institutional and regulatory guidelines. Subjects will be provided adequate

time to review the informed consent document and all questions will be answered to the satisfaction of the subject prior to signing the informed consent.

If the subject is willing to participate in the clinical investigation, he/she or an authorized legal representative must sign the informed consent form indicating that they have read and understand the information provided. Each site will follow their local IRB and applicable regulatory guidelines for obtaining informed consent. Documentation of the informed consent process for each subject and the original signed informed consent will be retained at the site and as required by applicable regulations.

